15.3.2. Safety Objective

The objective of the safety analysis is to provide safety information sufficient to characterize and summarize adverse events observed during the study.

15.4. Sample Size Considerations

A total sample size of 270 subjects is planned for the pivotal study cohort. The ENDObesity I study provided estimates for the mean %TBL of 14.5 (SD=5.8) at 6 months of follow-up. For the purposes of the sample size calculation, the assumed means were 13% in Treatment and 5% in Control subjects. This provides a difference (Treatment – Sham Control) in mean %TBL of 8% and the assumed standard deviation was increased to 9% (approximately 1.5 times that observed in the ENDObesity I study) to account for a more conservative estimate of the standard deviation. Under these assumptions, a sample size of 243 subjects (162 Treatment, 81 Control) has 90% power to reject H_0 under the 4% superiority margin scenario and 68.4% power under the superiority margin of 5%. Under less conservative scenario of standard deviation of 7, the study has 88% power to reject H_0 under the 5% superiority margin scenario and 99% power under the 4% superiority margin. The study will enroll 270 subjects (approximately 180 in the Treatment groups and 90 in the Control group) to compensate for losses to follow-up.

The second co-primary endpoint is to demonstrate the proportion of subjects with a $\geq 5\%$ TBL at 12 months is greater than 50%. Under the assumption of 65% responder rate in the Treatment group, the study requires 113 treatment subjects in order to have 90% power to reject null hypothesis for the second co-primary endpoint.

A third consideration for the sample size is the ability to provide reasonable safety data from the study. With the proposed sample size of 180 subjects in the Treatment group, there is an 80% likelihood to observe at least one event of any specific complication if it occurs in at a rate of 0.9% or greater in subjects treated with the TPSS. The upper limit of 95% exact binomial confidence interval for an event rate if none of 180 subjects has specific complication is 2.0%.

15.5. Statistical Analysis

15.5.1. Accountability and Demographics

The number of subjects in each population will be summarized overall and by site for each treatment group. In addition, the number of subjects completing the study and withdrawing from the study will be presented along with reasons for withdrawal.

Descriptive summaries for baseline and demographic characteristics including age, gender, height, weight, baseline BMI, medical history, and co-morbidities will be presented by treatment group.

15.5.2. Comparability of the Treatment Groups

The demographic and prognostic variables measured at study entry will be compared between the Treatment and the Control groups. Continuous variables will be compared with Student t-test for two independent samples or Wilcoxon rank sum test, and categorical variables will be compared with Fisher's exact test or Chi-square test.

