15.3. Study Objectives and Hypotheses

15.3.1. Primary Effectiveness Objective

The primary objective of this study is to assess the clinical effectiveness of the BAROnova TransPyloric Shuttle for weight reduction in patients with obesity, with a BMI of 35.0 to 40.0 kg/m², or a BMI of 30.0 through 34.9 kg/m² with one or more obesity-related comorbid conditions over the 12 months treatment period.

The hypothesis associated with the first co-primary endpoint is that the subjects in the Treatment group will have superior weight loss in %TBL compared to subjects in the Control group at 12-month follow up. The statistical null and alternative hypotheses are:

$$H_{i0}: \mu_T - \mu_C \leq \delta \text{ vs.}$$

$$H_{iA}: \mu_T - \mu_C > \delta,$$

Where,

μ_T is the mean % TBL at 12 months in the treated group

μ_C is the mean % TBL in the control group at 12 months.

δ is the superiority margin.

The hypotheses will be tested using a one-sided two-sample t-test for independent samples at the alpha level of 0.025. If the test value exceeds the nominal critical point, the H₀ will be rejected. The testing may be performed using mixed model repeated measurements approach. If the mixed model is used, the decision about the rejection of null hypothesis will be based upon the test for the 12-month follow-up outcomes. The primary statistical test will use $\delta = 0$. If the H₀ is rejected, the 95% confidence interval for the difference in %TBL between the groups will be created. The lower limit of the interval is the statistically achieved superiority margin.

The second co-primary effectiveness endpoint is the percentage of Treatment subjects with a $\geq 5\%$ TBL at 12 months. Proportion of subjects who lose at least 5% of their baseline weight will be compared against the target proportion of 50% using a one-sided test for hypothesized population proportion.

The statistical null and alternative hypotheses are:

$$H_{ii0}: p_T < \Pi_0 \text{ vs.}$$

$$H_{iiA}: p_T \geq \Pi_0,$$

Where,

p_T is the proportion in the study subjects from the Treatment group

Π_0 is the reference proportion (i.e 0.5 (50%))

Study statistical success is achieved if study null hypotheses for both co-primary endpoints are rejected. FDA recommends that the H_{i0} is rejected with superiority margin $\delta = 5\%$ and the H_{ii0} is rejected.

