15.5.3. Primary Analysis

The %TBL will be calculated as $(\text{Weight}(\text{kg})_{\text{BL}} - \text{Weight}(\text{kg})_{\text{FUP}}) / \text{Weight}(\text{kg})_{\text{BL}}$. Where $\text{Weight}(\text{kg})_{\text{BL}}$ is the subject's weight at baseline in kilograms and $\text{Weight}(\text{kg})_{\text{FUP}}$ is the subject's weight at follow-up in kilograms.

The %TBL will be summarized at each follow-up visit through 12 months along with the observed total body weight at baseline and each follow-up visit by treatment group.

The testing of null hypotheses for the co-primary efficacy endpoints is described in Section 15.3.1.

In order to accommodate missing data in the primary effectiveness analyses, a multiple imputation approach will be used to impute missing follow-up weight observations. A total of 5 imputed samples will be created. Covariates (e.g., gender) will be used in the imputation procedure in addition to the subject's weight from previous visits. The multiple imputation approach was first described by Rubin.³⁵ The SAS procedures MI and MIANALYZE will be used to create the imputations and perform the analysis. The statistical null hypotheses for both co-primary endpoints will be tested on multiply imputed data sets. Sensitivity analyses will be done by evaluating the primary analysis on the ITT and CC cohorts. Further, a last observation carry forward (LOCF) imputation will be performed for the sensitivity purposes.

Additionally, the %TBL median, mean and standard deviation and percent of subjects with greater than 5%TBL will be summarized by treatment group and levels of covariates. Covariates include gender (male versus female), race (Caucasian versus non-Caucasian), age (\leq median, $>$ median), and baseline BMI (30-34.9 kg/m² and 35-40.0 kg/m²).

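### Section 15.3.1 specifies no baseline adjustment for the %TBL comparison; pre-specifying one would modestly narrow the interval that sets the achieved margin, at almost no cost

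*Combined protocol and SAP*

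**What the plan says.** Section 15.3.1 gives the test for the first co-primary endpoint: "The hypotheses will be tested using a one-sided two-sample t-test for independent samples at the alpha level of 0.025". It then adds an option: "The testing may be performed using mixed model repeated measurements approach". If that option is taken, the decision rests on the 12-month result. No fixed effects or covariates are listed for the model, so adjustment is neither specified nor ruled out.

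The primary test uses a margin of zero. If it rejects, a 95% interval for the difference is formed, and "The lower limit of the interval is the statistically achieved superiority margin". The same section records that FDA recommends rejection with a margin of 5%.

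Baseline variables appear in four other places:

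- Section 15.5.1 lists age, gender, height, weight and baseline BMI for descriptive summary by arm.
- Section 15.5.2 says "The demographic and prognostic variables measured at study entry will be compared between the Treatment and the Control groups", using t, Wilcoxon, Fisher or chi-square tests. It names no variables and attaches no consequence to the result.
- Section 15.5.3 says "Covariates include gender (male versus female), race (Caucasian versus non-Caucasian), age" and goes on to baseline BMI in two classes. These serve descriptive summaries of %TBL by arm and level.
- Section 15.5.3 also uses covariates, with gender as the example, to impute missing weights. That fills gaps in the data but does not adjust the comparison of arms.

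Randomization is stratified by center only (Section 5.3).

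**The concern.** The plan collects variables that it regards as prognostic, tests them for imbalance and calls some of them covariates, but does not put them in the primary comparison. Two things are at stake.

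The first is precision. The interval is itself a result here, because its lower limit is the achieved margin. At the 5% margin the plan's own power is 68.4% with an SD of 9, so the width of the interval matters.

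The second is pre-specification. The t-test or mixed model choice is open, the mixed model has no listed terms, and baseline significance tests are scheduled. A small baseline p-value would invite an unplanned adjusted analysis, and then a dispute over which estimate defines the achieved margin. This second point does not depend on how prognostic the covariates are.

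**Working it through.** **Inputs.** From Section 15.4: "the assumed means were 13% in Treatment and 5% in Control subjects", a difference of 8 points; "the assumed standard deviation was increased to 9"%, with 7% as the less conservative case; 162 Treatment and 81 Control subjects. From Section 15.3.1: one-sided alpha 0.025. The R-squared of the baseline covariates for 12-month %TBL is not in the documents, so 2%, 5% and 10% are assumed.

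**Step 1: reproduce the plan's power.** SE = SD × sqrt(1/162 + 1/81) = 9 × 0.1361 = 1.225. Power comes from the noncentral t with 241 degrees of freedom and noncentrality (8 − margin)/SE.

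- SD 9, margin 4%: 90.2% (plan: 90%)
- SD 9, margin 5%: noncentrality 3/1.225 = 2.45, power 68.4% (plan: 68.4%)
- SD 7, margin 5%: 88.0% (plan: 88%)
- SD 7, margin 4%: 98.7% (plan: 99%)

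The figures match an unadjusted t-test, so the design counts no gain from covariates.

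**Step 2: the success test.** At margin zero and SD 9 the noncentrality is 8/1.225 = 6.53, and power exceeds 99.9% with or without adjustment.

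**Step 3: effect of adjustment at SD 9.** Residual SD = 9 × sqrt(1 − R²). The adjusted rows use 237 degrees of freedom, which allows for four covariates. The half-width is the t critical value (1.97) × SE. The lower limit is shown for an observed difference of 8.

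| Assumed R² | Residual SD | SE | 95% half-width | Lower limit | Power at 5% margin |
|---|---|---|---|---|---|
| 0 | 9.00 | 1.225 | 2.41 | 5.59 | 68.4% |
| 2% | 8.91 | 1.212 | 2.39 | 5.61 | 69.3% |
| 5% | 8.77 | 1.194 | 2.35 | 5.65 | 70.6% |
| 10% | 8.54 | 1.162 | 2.29 | 5.71 | 73.0% |

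The equivalent evaluable sample size is 243/(1 − R²), which is 248, 256 and 270. At SD 7 the power of 88.0% becomes 88.7%, 89.6% and 91.1%.

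**Step 4: how large an R² is plausible?** A single 50:50 factor with a difference of d points in %TBL explains R² = d²/(4 × 81) at SD 9. So R² of 2%, 5% and 10% needs d = 18 × sqrt(R²), about 2.5, 4.0 and 5.7 points. Several covariates could add up, but the documents give no figure that supports the top of this range.

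**Step 5: chance imbalance.** For a factor present in half of subjects, the between-arm difference in its proportion has SD sqrt(0.25 × (1/180 + 1/90)) = 6.5 percentage points. If the factor shifts %TBL by an assumed 2 points, the treatment difference moves by 0.065 × 2 = 0.13 points. The SE at 180:90 is 9 × sqrt(1/180 + 1/90) = 1.16, so the shift is about 11% of one standard error.

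**The case against.** The strongest reply is that nothing here is an error. After randomization an unadjusted two-sample comparison is valid, its standard error already allows for chance imbalance, and the plan's power was calculated for that test. This stands: the point concerns efficiency and pre-specification. A reader might infer bias or an inflated error rate, but the documents show neither.

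A reader might also infer that the plan shuts covariates out of the primary analysis. It does not. The permitted mixed model could carry them, and the text is simply silent on its terms.

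The gain may be small. %TBL already divides by baseline weight (Section 15.5.3), and eligibility restricts BMI to 30–40 and age to 22–60 (Section 7.2), so R-squared may well be low. This stands too. Nor would adjustment in the assumed range repair the 68.4%. Reaching 80% at the 5% margin needs a residual SD of about 7.87, an R-squared of 1 − (7.87/9)² = 0.24.

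That Section 15.5.2 has no consequence for the analysis is not a fault in itself, since choosing the model from baseline p-values would be worse. The section names no variables, so it cannot be said that race is tested there. Finally, the subgroup summaries in Section 15.5.3 let a reader see outcomes by level, but they are descriptive and supply no adjusted estimate.

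**Conclusion.** The point holds as a low-cost improvement. Section 15.3.1 specifies no baseline adjustment for the %TBL comparison, although gender, age and baseline BMI are collected and named as covariates. Under the plan's SD of 9 and 162:81 evaluable subjects, adjustment would add 0.9, 2.2 or 4.6 points of power at the 5% margin for an R-squared of 2%, 5% or 10%. It would raise the achieved margin by 0.02, 0.06 or 0.12 points.

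These sizes rest on assumed R-squared values and on complete data at the design sample size; they do not model the multiple imputation. The benefit is confined to the achieved margin and the 5% margin that FDA recommends. The zero-margin test is essentially unaffected, and the second co-primary endpoint, a single-arm proportion, is outside this point. A reader might infer that study success is at risk without adjustment; the design figures do not support that.

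**What to change.** In Section 15.3.1, name one model as the single source of the estimate, the one-sided test and the 95% interval for the difference in %TBL. It should be either a linear model at 12 months fitted in each imputed data set and pooled, or the mixed model if that is retained. List its terms: treatment, continuous baseline BMI or weight, gender and age. Put the same covariates in the imputation model, which Section 15.5.3 leaves open. State at the same time whether center, the only stratification factor, is a term; that is a separate question, but it belongs in the same sentence of the SAP.

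Keep the unadjusted t-test as a sensitivity analysis. In Section 15.5.2, say that baseline p-values will not guide adjustment, or replace them with descriptive summaries.

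The cost is SAP wording and a few degrees of freedom out of about 240. No new data are needed.

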15.5.3. Primary Analysis

The %TBL will be calculated as $(\text{Weight}(\text{kg})_{\text{BL}} - \text{Weight}(\text{kg})_{\text{FUP}}) / \text{Weight}(\text{kg})_{\text{BL}}$. Where $\text{Weight}(\text{kg})_{\text{BL}}$ is the subject's weight at baseline in kilograms and $\text{Weight}(\text{kg})_{\text{FUP}}$ is the subject's weight at follow-up in kilograms.

The %TBL will be summarized at each follow-up visit through 12 months along with the observed total body weight at baseline and each follow-up visit by treatment group.

The testing of null hypotheses for the co-primary efficacy endpoints is described in Section 15.3.1.

In order to accommodate missing data in the primary effectiveness analyses, a multiple imputation approach will be used to impute missing follow-up weight observations. A total of 5 imputed samples will be created. Covariates (e.g., gender) will be used in the imputation procedure in addition to the subject's weight from previous visits. The multiple imputation approach was first described by Rubin.³⁵ The SAS procedures MI and MIANALYZE will be used to create the imputations and perform the analysis. The statistical null hypotheses for both co-primary endpoints will be tested on multiply imputed data sets. Sensitivity analyses will be done by evaluating the primary analysis on the ITT and CC cohorts. Further, a last observation carry forward (LOCF) imputation will be performed for the sensitivity purposes.

Additionally, the %TBL median, mean and standard deviation and percent of subjects with greater than 5%TBL will be summarized by treatment group and levels of covariates. Covariates include gender (male versus female), race (Caucasian versus non-Caucasian), age (\leq median, $>$ median), and baseline BMI (30-34.9 kg/m² and 35-40.0 kg/m²).

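### Five imputations and no stated seed leave avoidable Monte Carlo noise in the lower limit that the plan reports as the achieved superiority margin

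*Combined protocol and SAP*

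**What the plan says.** Section 15.5.3 imputes missing follow-up weights for the primary effectiveness analyses. The number is fixed: "A total of 5 imputed samples will be created". On the model, it says that covariates such as gender "will be used in the imputation procedure in addition to the subject's weight from previous visits". On software: "The SAS procedures MI and MIANALYZE will be used to create the imputations and perform the analysis". On scope: "The statistical null hypotheses for both co-primary endpoints will be tested on multiply imputed data sets". The same analysis is repeated on the ITT and completed-case populations as sensitivity analyses. The section gives no seed, no check of Monte Carlo error and no rule for raising the number of imputations.

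Section 15.3.1 specifies a "one-sided two-sample t-test for independent samples at the alpha level of 0.025" for the first co-primary endpoint. "The primary statistical test will use" δ = 0. If that null is rejected, a 95% confidence interval is formed, and "The lower limit of the interval is the statistically achieved superiority margin". The section also records FDA's recommendation that the first null "is rejected with superiority margin" 5%.

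**The concern.** The plan treats one output of a random procedure as a result in its own right: the lower limit is the margin achieved, and a regulator will compare it with 5%. With few imputations that limit depends on the random draws as well as on the data. If the seed-to-seed movement is not small beside the distance between the expected limit and 5%, the same data can give a limit on either side of 5% according to the seed. With no seed in the plan, the reported figure also cannot be reproduced from the plan alone, and there is no written defence against the suggestion that a favourable run was chosen.

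**Working it through.** **Inputs from Section 15.4.** Means 13% and 5% (difference 8); SD 9, or 7 in the less conservative scenario; 243 evaluable subjects (162:81) out of 270 enrolled (180:90). Implied loss: 1 − 243/270 = 10%.

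**Assumptions not in the documents.** Correlation between the prior-visit and 12-month %TBL of 0.6 to 0.85; missingness of 20% and 30% as alternatives to 10%; all 270 subjects in the per-protocol population.

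**Step 1: reproduce the plan's power.** With 162:81, one-sided 0.025 and noncentral t on 241 df, SD 9 gives 90.2% (4% margin) and 68.4% (5% margin). SD 7 gives 88.0% (5%) and 98.7% (4%). The plan states 90, 68.4, 88 and 99%, so its figures reproduce.

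**Step 2: expected lower limit.** Limit = 8 − 1.96 × SD × √(1/n_T + 1/n_C).
- SD 9, 162:81: SE 1.225; 8 − 2.40 = 5.60.
- SD 9, 180:90: SE 1.162; 8 − 2.28 = 5.72.
- SD 7, 162:81: SE 0.953; 8 − 1.87 = 6.13.
- SD 7, 180:90: SE 0.904; 8 − 1.77 = 6.23.

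The gap to 5% is 0.6 to 0.7 points at SD 9 and 1.1 to 1.2 points at SD 7.

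**Step 3: seed-to-seed movement of the limit.** Bayesian regression imputation was combined by Rubin's rules, with T = W + (1 + 1/m)B and a t reference on Rubin's df. There were 180:90 subjects with SD 9, and each of 30 simulated data sets was re-imputed under 300 seeds. Entries are the seed SD of the lower limit in %TBL points, with the width covering 95% of seeds in brackets.

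| Missing | Correlation | m = 5 | m = 50 | m = 100 |
|---|---|---|---|---|
| 10% | 0.85 | 0.099 (0.38) | 0.031 (0.12) | 0.022 (0.08) |
| 10% | 0.6 | 0.164 (0.63) | 0.049 (0.19) | 0.034 (0.13) |
| 20% | 0.85 | 0.164 (0.62) | 0.048 (0.19) | 0.034 (0.13) |
| 20% | 0.6 | 0.274 (1.07) | 0.078 (0.30) | 0.053 (0.21) |
| 30% | 0.85 | 0.221 (0.87) | 0.064 (0.25) | 0.046 (0.18) |
| 30% | 0.6 | 0.392 (1.53) | 0.106 (0.41) | 0.076 (0.29) |

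A repeat simulation with m = 5 gave 0.10–0.16, 0.16–0.28 and 0.22–0.41 at 10, 20 and 30% missing. If earlier weights carried no information (correlation 0), the m = 5 values would be 0.22, 0.37 and 0.57.

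**Step 4: where the movement comes from.** At 10% missing and m = 5 the seed SD of the point estimate is 0.143 (correlation 0.6) and 0.093 (0.85). Its share of the limit's seed variance is (0.143/0.164)² = 76% and (0.093/0.099)² = 88%. At 30% missing the shares are (0.274/0.392)² = 49% and (0.179/0.221)² = 66%. At the plan's own loss rate, then, most of the noise is in the point estimate; the width of the interval contributes less.

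**Step 5: how often two seeds disagree about 5%.** Direct simulation gives roughly 2 to 6% of trials at 10% missing and 4 to 15% at 20 to 30% missing, with m = 5. A hand approximation is (density of the limit at 5 across trials) × 2s/√π, where s is the seed SD.
- 10% missing, correlation 0.6: SE 1.21, expected limit 8 − 1.96 × 1.21 = 5.63, density 0.288; 0.288 × 1.128 × 0.164 = 5.3%.
- 10% missing, correlation 0.85: SE 1.164, expected limit 5.72, density 0.283; 0.283 × 1.128 × 0.099 = 3.2%.
- 30% missing, correlation 0.6: SE 1.331, expected limit about 5.35, density 0.290; 0.290 × 1.128 × 0.392 = 12.8%.

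These agree with the simulation. With m = 50 the simulated disagreement is about 1% at 10% missing and about 1 to 5% at 20 to 30%.

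**Step 6: second co-primary endpoint.** The seed SD of the lower limit of the proportion at m = 5 is 0.4 to 1.5 percentage points over all scenarios. At 65% of 180, the expected lower limit is 65 − 1.96 × √(65 × 35/180) = 65 − 7.0 = 58.0%, which is 8 points above the 50% target.

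**The case against.** The strongest reply is that nothing decisive depends on this, and much of that reply stands.

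- A reader might infer that 5 imputations make the interval or the test invalid. They do not. MIANALYZE applies Rubin's variance and t reference, which allow for a finite number of imputations. The issue is precision and reproducibility.
- A reader might infer that formal success turns on the seed. Section 15.3.1 tests δ = 0, and the 5% margin is recorded as FDA's recommendation. Under the planning assumptions an expected limit of 5.6 is more than 13 times the largest seed SD found at correlations of 0.6 to 0.85 (5.6/0.41 = 13.7).
- A reader might blame the variance estimate on 4 degrees of freedom. Step 4 shows that this is the smaller part at 10% missing.
- A reader might infer that both co-primary endpoints are materially affected. Step 6 shows that the effect on the second is small.
- With SD 7, which Section 15.4 also considers, the gap is at least 1.1 points, and two seeds disagree in only about 1 to 2% of trials (10 to 20% missing, correlation 0.85).
- Section 15.3.1 permits a mixed model for the first test, which need not use imputation. This is only partial relief, because Section 15.5.3 still tests both nulls on imputed data.

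Missingness above 10% is an assumption. It is possible, because Section 7.5 ends participation at early device removal and Section 10.5 has control subjects exit on the same basis, but no figure is given.

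**Conclusion.** The point holds as an avoidable imprecision in a reported figure. At the plan's implied 10% loss, with SD 9 and a correlation of 0.6 to 0.85, the declared margin has a seed SD of about 0.10 to 0.16 points. The 95% seed range is about 0.4 to 0.6 points, against an expected gap to 5% of 0.6 to 0.7. Two seeds would disagree about clearing 5% in roughly 2 to 6% of trials. At an assumed 20 to 30% missing, the seed SD is about 0.16 to 0.41 and disagreement about 4 to 15%. The correlation and the higher missingness are assumptions, and the sizes scale with them. The documents do not support the stronger conclusion that the primary test or its interval is unsound.

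**What to change.** In Section 15.5.3, replace 5 with at least 50 imputed data sets (for example 100) and state the seed. Apply both to the two co-primary analyses and to the ITT sensitivity analysis. With 50 imputations the seed SD of the limit falls by a factor of 3.2 to 3.7 in the table above (for example 0.164/0.049 = 3.3 at 10% missing, correlation 0.6); with 100 it falls by 4.5 to 5.2. Both changes are needed: a seed alone would make one noisy draw repeatable without making it more precise. The cost is one number, one added line and some minutes of computing, with no change to data collection, sample size or alpha.
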